An AE is any undesirable medical event occurring to a subject in a clinical trial, whether or not related to the trial product(s). This includes events reported from the first trial related activity after the subject has signed the informed consent and until post treatment follow-up period as defined in the protocol. The following should not be recorded as AEs, if recorded as medical history/concomitant illness on the CRF at screening:

- Pre-planned procedure, unless the condition for which the procedure was planned has worsened from the first trial related activity after the subject has signed the informed consent
- Pre-existing conditions found as a result of screening procedures

Clinical Laboratory Adverse Event:

A clinical laboratory AE is any clinical laboratory abnormality regarded as clinically significant i.e. an abnormality that suggests a disease and/or organ toxicity and is of a severity, which requires active management, (i.e. change of dose, discontinuation of trial product, more frequent follow-up or diagnostic investigation).

Serious Adverse Event (SAE):

A serious AE is an experience that at any dose results in any of the following:

- Death
- A life-threatening experience (an event in which the subject was at risk of death at the time of the event. It does not refer to an event which hypothetically might have caused death if it was more severe)
- In-patient hospitalisation or prolongation of existing hospitalization
- A persistent or significant disability/incapacity
- A congenital anomaly/birth defect
- Important medical events that may not result in death, be life-threatening*, or require hospitalization may be considered an SAE when, based upon appropriate medical judgement, they may jeopardize the subject and may require medical or surgical intervention to prevent one of the outcomes listed in this definition.
- Suspicion of transmission of infectious agents must always be considered an SAE

Note: The term life-threatening in the definition of serious refers to an event in which the patient was at risk of death at the time of the event. It does not refer to an event, which hypothetically might have caused death if it was more severe.

Serious Adverse Drug Reaction (SADR):

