An adverse drug reaction (ADR) is an adverse event for which a causal relationship (Possible/Probable relation) between the trial drug and the occurrence of the event is suspected. The ADR should be classified as serious if it meets one or more of the seriousness criteria.

Suspected Unexpected Serious Adverse Reaction (SUSAR):

An SAE which is unexpected and regarded as possibly or probably related to the trial product by the investigator.

1250 **Non-Serious Adverse Event:**

1251 A non-serious AE is any AE which does not fulfil the definition of an SAE.

1252

1253 **Severity Assessment Definitions:**

- 1254 • Mild: Transient symptoms, no interference with the subject's daily activities
- 1255 • Moderate: Marked symptoms, moderate interference with the subject's daily activities
- 1256 • Severe: Considerable interference with the subject's daily activities, unacceptable

1257

1258 **Relationship to trial medication Assessment Definitions:**

- 1259 • Probable: Good reasons and sufficient documentation to assume a causal relationship
- 1260 • Possible: A causal relationship is conceivable and cannot be dismissed
- 1261 • Unlikely: The event is most likely related to an etiology other than the trial product
- 1262 • Suggested to specify the reference document (eg: USPI, CCDS) in the protocol which is
- 1263 agreed upon with NN, for evaluation of expectedness

1264

1265 **Outcome Categories and Definitions:**

- 1266 • Recovered: Fully recovered or by medical or surgical treatment the condition has returned to the level observed at the first trial related activity after the subject signed the informed consent
- 1267 • Recovering: The condition is improving and the subject is expected to recover from the event. This term should only be used when the subject has completed the trial
- 1268 • Recovered with sequelae: As a result of the AE, the subject suffered persistent and significant disability/incapacity (e.g. became blind, deaf, paralyzed). Any AE recovered with sequelae should be rated as an SAE
- 1269 • Not recovered
- 1270 • Fatal – this term is only applicable if the subject died from a condition related to the reported AE. Outcomes of other reported AEs in a subject before he/she died should be assessed according to the state of the event at the time of death. An AE with fatal outcome must be reported as an SAE.
- 1271 • Unknown

1272

1273 **Collection, Recording and Reporting of Adverse Events**

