1274 All events meeting the definition of an adverse event will be collected and reported from the first trial related activity after the subject has signed the informed consent and until the end of the post-treatment follow-up period as stated in the protocol.

1275

1276 **Plan for reporting both anticipated and unanticipated adverse events:**

1277 Each subject will be evaluated for any adverse events. Any event that is reported to either the principal investigator or his designated research associates by the subject or medical staff caring for the subject and which meets the criteria will be documented as such. Any event that is reported will then generate an adverse event report, which will be submitted to the safety officer, local IRB, Novo Nordisk, and FDA. The report will include a description of the event, when and how it was reported, as well as any official chart records or documentation to corroborate the event or the reporting of the event. All adverse events will be graded as mild, moderate, or severe. All unexpected fatal or life-threatening suspected adverse reactions represent especially important safety information and will be reported to FDA as soon as possible but no later than 7 calendar days following the sponsor's initial receipt of the information. Any severe and/or unanticipated adverse event will be reported to the safety officer, local IRB, Novo Nordisk, and FDA within 24 hours of knowledge of the event. At a minimum, the investigator will copy NN when expediting SARs or SUSARs to health authorities and will

1299 report all SARs related to NN product to the local NN affiliate safety department. All other
1300 adverse events will be reported in a timely fashion to the safety officer, local IRB, Novo Nordisk,
1301 and FDA preferably within 2 weeks of the date of the event. All adverse events will be
1302 summarized annually and submitted to the local IRB, Novo Nordisk, and FDA. Any action
1303 resulting in a temporary or permanent suspension of this trial (e.g. FDA actions, IRB actions, or
1304 actions by the investigators or co-investigators) will be reported to the appropriate Novo Nordisk
1305 program official.

1306

Follow-up of Adverse Events

1308 Periodic reviews of adverse events and safety issues will be performed during the trial as listed
1309 below:

1310

1311 Safety reviews. The principal investigators (SM, IN) will review the safety and progress of this
1312 trial on a weekly basis.

1313

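### The 24-hour reporting rule is triggered by severity, not seriousness, so an anticipated SAE graded mild or moderate has no firm reporting deadline

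*Protocol*

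**What the plan says.** All the relevant rules are in the protocol's adverse event chapter.

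- **Seriousness** (Serious Adverse Event) is defined by outcome. One criterion is "In-patient hospitalisation or prolongation of existing hospitalization". None of the criteria refers to the intensity grade.
- **Severity** (Severity Assessment Definitions) is a three-level intensity scale. Its top level begins "Severe: Considerable interference with the" and continues with the subject's daily activities.
- **Grading** (plan for reporting anticipated and unanticipated events): "All adverse events will be graded as mild, moderate, or severe".
- **Fast route** (same paragraph): the trigger is "Any severe and/or unanticipated adverse event", and the rule reads "Any severe and/or unanticipated adverse event will be reported to the safety officer, local IRB, Novo Nordisk, and FDA within 24 hours of knowledge".
- **Residual route** (same paragraph): all other "adverse events will be reported in a timely fashion to the safety officer, local IRB, Novo Nordisk", "and FDA preferably within 2 weeks of the date of the event".

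Two more sentences in that paragraph concern expedited reporting. One sets a 7-day limit to the FDA for suspected reactions that are both unexpected and either fatal or life-threatening. The other asks the investigator to copy the supplier when expediting SARs or SUSARs to health authorities, and to report SARs related to the supplier's product to its safety department. It gives no time limit.

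**The concern.** The 24-hour sentence closely follows the sentence that grades events as mild, moderate or severe, so its trigger word can only be read as the intensity grade. Under the protocol's own definitions that is not the same as seriousness. A subject admitted to hospital for a listed side effect has an SAE whatever its intensity. If staff grade it moderate and regard it as anticipated, the fast route does not apply.

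Staff could then follow the protocol to the letter while the safety officer, IRB, supplier and FDA learn of an SAE much later than 24 hours. The residual limit is counted from the date of the event, and its wording makes it a preference, so it is not a firm outer limit. What is at stake is the timeliness of safety oversight. Power, alpha and the primary analysis are not touched.

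**Working it through.** The protocol gives no figure to reproduce here. The check applies the reporting rules as written to every type of event.

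**Inputs.** Seriousness has two values (yes, no), intensity three (mild, moderate, severe) and expectedness two (anticipated, unanticipated), so there are 2 × 3 × 2 = 12 combinations.

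**Routing as written**

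| Event type | Serious | Non-serious | Route |
|---|---|---|---|
| Severe, anticipated or unanticipated | 2 | 2 | 24 hours |
| Mild or moderate, unanticipated | 2 | 2 | 24 hours |
| Mild or moderate, anticipated | 2 | 2 | Residual, about 2 weeks |

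The fast route takes 4 + 4 = 8 of 12 combinations and the residual route takes 4. Of the 6 serious combinations, 2 + 2 = 4 are in the fast route and 2 are in the residual route. These are counts of event types, not frequencies.

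**Does another clause catch the two?**

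- The 7-day sentence requires the event to be unexpected, so it does not apply to an anticipated one.
- The SAR/SUSAR sentence would apply if the event were judged possibly or probably related. It presupposes expediting to health authorities and adds a report to the supplier, but sets no deadline.
- Outcome Categories and Definitions says that a fatal event must be reported as an SAE, but no SAE timeline is attached.
- The weekly review by the principal investigators and the twice-yearly DSMC meetings set no external deadline for a single event.

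I could not see the text between Premature Termination of Trial and the reference list. The adverse event chapter ends before that point.

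**Example.** Possible Side-Effects lists vomiting, gallbladder disease and acute pancreatitis. A hospital admission for gallbladder disease, graded moderate and treated as anticipated because it is listed, meets the SAE definition but neither 24-hour trigger.

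**Upper bound on subjects affected.** The protocol plans 178 randomized 1:1, so 178 / 2 = 89 per arm. Tolerability and Adverse Events gives SAE rates from earlier obesity trials of 4.2% on liraglutide and 2.4% on placebo.

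- Liraglutide: 89 × 0.042 = 3.7
- Placebo: 89 × 0.024 = 2.1
- Total: 3.7 + 2.1 = 5.8, about 6 subjects with any SAE

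The document does not split SAEs by intensity or expectedness. The affected number therefore lies anywhere from 0 to about 6, if those rates carry over.

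**Routing after adding serious to the trigger.** The two serious combinations move to the fast route, giving 6 of 6 serious. The non-serious combinations stay at 4 of 6. Replacing severe by serious would also give 6 of 6 serious, but would cut the non-serious ones from 4 to 3, because an anticipated, severe, non-serious event would lose its 24-hour report.

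**The case against.** The strongest reply is that the gap is narrow. An event must be serious, anticipated and graded below severe, all at once. An in-patient stay will often interfere considerably with daily life, be graded severe and so trigger the 24 hours. The protocol also does not define unanticipated. The note under the relationship definitions, which suggests naming a reference document for expectedness, was left unresolved, so a hospitalised case of a listed symptom might be judged unanticipated. In addition, AEs and SAEs are reviewed at every visit, and the principal investigators review safety weekly.

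All of this limits how often the gap would matter, and it stands to that extent. It does not close the gap: no clause gives these SAEs a firm deadline, and without a named reference document the expectedness trigger is an uncertain backstop.

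A reader might infer more than the document supports:

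- **That about 6 SAEs would be reported late.** Six is the expected number of subjects with any SAE. The misrouted subset is unknown and may be empty. The rates come from earlier trials, the main ones lasting 56 weeks against 40 weeks on treatment here.
- **That the events of most interest escape.** Ascertainment of clinical safety endpoints names death, myocardial infarction and stroke. None is on the side-effect list, so if that list defines what is anticipated, they already have the 24-hour clock.
- **That related SAEs are never expedited.** The SAR/SUSAR sentence presupposes that they are. What is missing is a time limit.
- **That the fast route would fill with nausea reports.** The 47.6% nausea rate covers a single earlier trial and gives no severe fraction. Sending severe non-serious events within 24 hours is a cautious choice that contradicts nothing.

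**Conclusion.** The point holds in a limited form. As written, SAEs that are anticipated and graded mild or moderate have only a non-binding two-week route to the safety officer, IRB, supplier and FDA. That is 2 of the 6 serious combinations. The affected number of subjects is between zero and about 6, the upper end resting on the background SAE rates applying to 89 per arm.

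The conclusion assumes that severe carries the meaning the protocol gives it, and that a listed side effect can count as anticipated. That the authors meant serious is plausible but is an inference; the text shows only which word was used. The point deserves correction because the remedy is trivial and concerns subject safety. It has no bearing on the efficacy analysis.

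**What to change.** Add serious, with a reference to the protocol's own SAE definition, to the existing 24-hour trigger, so that it covers any adverse event that is serious, severe or unanticipated. Keep the other two triggers: dropping severe would withdraw reports that are now required, and a new term such as unanticipated problem would be undefined in this protocol. Check the severity, seriousness and reporting sections against each other when amending.

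The cost is a one-sentence amendment and at most a few additional 24-hour reports over the trial. No new procedure or data collection is needed.

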597 2. Participants can be withdrawn from the trial at the discretion of the Investigator due to
 598 safety concerns of if judged to be non-compliant with the trial protocol.

599 3. Pregnancy or intention of becoming pregnant

600 4. If target treatment dose of the randomized product is not tolerated by the subject.

601 5. If the trial investigator suspects acute pancreatitis, the trial drug will be discontinued until
 602 the confirmatory tests (clinically indicated laboratory and imaging) have been conducted
 603 and appropriate treatment has been administered. We anticipate confirmation within 72
 604 hours. If acute pancreatitis is confirmed, the participant will be withdrawn from the trial.
 605 If acute pancreatitis is not confirmed, the participant will resume the trial drug at the
 606 same dose previously used before temporary discontinuation.

607 6. Temporary trial drug discontinuation criteria:
 608 - Side effects to trial medication (until such side effects have resolved or have
 609 been otherwise addressed)
 610 - Acute illness requiring treatment or hospitalization
 611 - The longest time that the subject can be off trial drug and still continue in the trial
 612 is 4 weeks. If the trial drug is discontinued for >72 hours, then the dosing
 613 escalation regimen will be restarted at 0.6 mg daily and titrated up according to
 614 prescribing information recommendations.

616 **Subject Replacement**

617 Participants will not be replaced if they withdraw or become ineligible but they will be asked to
 618 return at the end of the trial period to complete the follow-up imaging/laboratory testing and
 619 analyzed in an intention to treat analysis. As up to a 28% drop-out rate is anticipated, enrolment
 620 will account for expected drop-out to minimize loss to follow-up given that subjects will not be
 621 replaced.

623 **Rationale for Trial Population**

624 The trial population represents the target population for which liraglutide is approved for chronic
 625 weight management in adult patients, with the additional inclusion criterion of a diagnosis of
 626 metabolic syndrome. This important criterion has been selected to enrich the trial population
 627 with participants with a high visceral adipose tissue burden in order to improve the statistical
 628 power to observe a meaningful effect on visceral adipose mass and enrich the trial population
 629 with individuals at high risk for cardiovascular disease.

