631 **Imaging Assessments**

632 The primary and secondary endpoints of visceral fat, abdominal subcutaneous fat, lower body
 633 fat, liver fat, and total body fat and fat-free (lean) mass will be assessed using a Phillips 3T MRI
 634 system utilizing a two point Dixon fat-water segmentation technique (Advanced MR Analytics,
 635 Sweden).²¹ This MRI system has been extensively studied and validated in multiple cohorts,²¹⁻²³
 636 has excellent test/retest precision and reliability,²⁴ and is rapid (<6 minutes) and therefore cost
 637 effective.

638 **STATISTICAL CONSIDERATIONS:**

641 **Sample Size Calculation:**

642 This trial is powered to detect a clinically meaningful difference in the placebo-corrected relative
 643 reduction in VAT. The estimates used in the sample size calculations below are derived from

644 prior data from the SCALE program. Assuming a mean 8% relative reduction of VAT among
 645 placebo treated subjects and an expected 16% relative reduction of VAT among liraglutide
 646 treated subjects (with a standard deviation of 16%, based on data from [2]), we expect to require
 647 128 total subjects (in a 1:1 trial drug:placebo randomization scheme) to achieve 80% power to
 648 detect an 8% difference between groups at an alpha level of 0.05. Assuming an estimated 28%
 649 of subjects may withdraw trial medication during the trial, we expect a planned total of 178
 650 patients will be randomized in order to achieve at least 128 completers of the full trial protocol.
 651

Placebo-corrected Effect Size	Power		
	80%	85%	90%
Sample Size (Total N, 1:1 randomization)			
5%	322	368	432
8%	128	146	170
10%	82	92	108

652
 653 **Statistical Methods:** A formal statistical analysis plan will follow. Briefly, baseline
 654 characteristics between liraglutide and placebo treated groups will be compared using
 655 appropriate parametric or non-parametric tests depending on the distribution of the data. The
 656 primary outcome will be analyzed using an intention to treat analysis. Mean change in outcome
 657 measurements will be compared between groups using the appropriate statistical test.
 658 Outcomes will also be analyzed by subgroups including age (above/below median), sex, race
 659 (non-Hispanic black, non-Hispanic white, and Hispanic), BMI category (overweight, class I
 660 obese, class II/III obese), and prediabetes status (yes/no). In order to minimize type II error in

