- 1350 • More frequent (>10%): nausea, diarrhea, constipation, and vomiting;
- 1351 • Less common (1-10%): dyspepsia, abdominal pain, abdominal distension, eructation,
 1352 flatulence; and
- 1353 • Rarely (<1%): gallbladder disease, acute pancreatitis

1354 All adverse effects are reversible with discontinuation of the medication.

1355 **Data and Safety Monitoring Committee (DSMC):**

- 1357 1. [name]
- 1358 2. [name]
- 1359 3. [name]
- 1360 4. [name]

1361 The DSMC will meet biannually by telephone/teleconference and distribute a report to the IRB
 1362 at the completion of each meeting.

1363 **LIABILITY AND SUBJECT INSURANCE:**

1364 During and following a subject's participation in the trial, the primary investigators (IN and SM)
 1365 and UT Southwestern Medical Center will provide adequate medical care to the study subject
 1366 for any study-related adverse events, including clinically significant laboratory values related to
 1367 the study. This medical care for study subjects will be provided regardless of their insurance
 1368 status.

1369
 1370 Novo Nordisk carries product liability insurance for its products. Sponsor-investigator agrees to
 1371 indemnify Novo Nordisk in accordance with the written contract executed between the parties
 1372 for this study. Generally, however, Novo Nordisk assumes no liability in the event of negligence
 1373 of the sponsor-investigator conducting the trial, or by persons for whom the sponsor-investigator
 1374 is responsible.

1375 **EVALUABILITY OF SUBJECTS:**

1376 The following analysis sets are defined:

1377 ***Full analysis set (FAS)***

1378 All randomized subjects exposed to at least one dose of the trial product and with at least one
 1379 post-baseline assessment of any efficacy endpoint will be included. Subjects in the FAS will be
 1380 analyzed according to intention to treat (primary) and per-protocol (secondary). The requirement
 1381 of a post-baseline observation is in alignment with the FDA recommendations.

1382 ***Safety analysis set***

1383 All randomized subjects who have been exposed to at least one dose of trial product. Subjects
 1384 in the safety analysis set will be analyzed "as treated".

1385 **PREMATURE TERMINATION OF TRIAL:**

1386 The trial will be prematurely terminated for the following reasons only:

- 1387 1. A serious threat to the safety of trial participants occurs that cannot be addressed in any

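### The primary analysis is called intention to treat, but the full analysis set requires a dose and a post-baseline value, so it is a modified intention-to-treat set and no all-randomised set is defined

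*Protocol*

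**What the plan says.** Three places in the protocol define who enters the primary analysis.

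- **Statistical Methods:** the "primary outcome will be analyzed using an intention to treat analysis". No exclusion is named.
- **Subject Replacement:** "Participants will not be replaced if they withdraw or become ineligible but they will be asked to" return for end-of-trial imaging and laboratory tests, and are to be "analyzed in an intention to treat analysis". This covers subjects who withdraw and subjects who become ineligible.
- **Evaluability of Subjects, Full analysis set:** the set is "All randomized subjects exposed to at least one dose of the trial product and with at least one" "post-baseline assessment of any efficacy endpoint will be included. Subjects in the FAS will be" "analyzed according to intention to treat (primary) and per-protocol (secondary). The requirement". The second condition is defended: the requirement "of a post-baseline observation is in alignment with the FDA recommendations". No reason is given for the dose condition.

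The only other set defined is the safety set, which is analysed as treated. There is no all-randomised set.

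Two other sections matter. Visit Procedures asks subjects who discontinue early to attend Visit 16x, 40 weeks after randomisation, so that all outcomes can be recorded. Missing Data plans imputation, last observation carried forward, mixed-model approaches and sensitivity analyses.

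**The concern.** Intention to treat means that every randomised subject is analysed in the assigned arm. A set that depends on taking a dose and on supplying a later measurement is selected by events after randomisation, so the comparison is no longer fully protected by randomisation. The protocol cannot both include everyone who withdraws or becomes ineligible and apply these two conditions.

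Three things are at stake. The result would be reported under a label it does not have. A measured primary outcome could be discarded. And subjects with identical VAT data would be treated differently according to whether they reached the first post-baseline visit. If very early loss depended on treatment, removing those subjects could also favour liraglutide.

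The SAP is not at hand, but this is not a matter left to it. The protocol itself fixes the set.

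**Working it through.** **1. The plan's own figures.** Inputs from Sample Size Calculation: VAT change −16% on liraglutide and −8% on placebo, SD 16%, two-sided alpha 0.05, 80% power, 1:1 allocation, 28% withdrawal.

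- Normal approximation: n per arm = 2 × (1.96 + 0.842)² × 16² / 8² = 62.8, so 63 per arm and 126 in total.
- Two-sample t-test: 64 per arm, 128 in total, as stated.
- Inflation: 128 / (1 − 0.28) = 177.8, so 178, as stated.

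These figures are sound, and the point below does not alter them.

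**2. The sections side by side.** VAT by MRI is scheduled only at randomisation and at end of treatment (table of visits with assessments). Weight, blood pressure and heart rate are also listed endpoints and are measured from Visit 4, week 1.

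| Randomised subject | Week-40 VAT | Statistical Methods and Subject Replacement | FAS |
|---|---|---|---|
| Never injects (for example, found ineligible before the first dose), attends Visit 16x | measured | analysed | excluded: no dose |
| Takes a dose, no post-baseline assessment at all | missing | analysed, as missing | deleted |
| Takes a dose, seen at week 1, then lost | missing | analysed, as missing | kept, as missing |
| Takes a dose, stops early, attends Visit 16x | measured | analysed | kept |

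The first two rows contradict each other across sections. Rows two and three hold the same VAT information, baseline only, yet one is deleted and the other goes to the missing-data method. The post-baseline condition therefore does not select subjects with usable primary data.

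**3. How many, and how much.** The protocol gives no rate for either exclusion. As an assumed range, 1%, 2%, 5% or 10% of 178 is about 2, 4, 9 or 18 subjects.

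To illustrate a possible effect, suppose the FAS shows the planned difference of −8.00 points. For each arm, all-randomised mean = (1 − p) × FAS mean + p × mean of those excluded. All values of p and all outcomes of the excluded are assumptions.

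| Excluded, liraglutide / placebo | Assumed change in the excluded | Liraglutide mean | Placebo mean | All-randomised difference |
|---|---|---|---|---|
| 2% / 1% | −8 | 0.98(−16) + 0.02(−8) = −15.84 | −8.00 | −7.84 |
| 5% / 2% | −8 | 0.95(−16) + 0.05(−8) = −15.60 | −8.00 | −7.60 |
| 8% / 3% | 0 | 0.92(−16) = −14.72 | 0.97(−8) = −7.76 | −6.96 |

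Over these cases the gap between the FAS and the all-randomised result is 0.16 to 1.04 points. The standard error of the difference at 64 per arm is 16 × √(2/64) = 2.83, so the middle case, 0.40, is about 0.14 of a standard error.

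The gap is an input rather than a finding. With 5% excluded from both arms and a −8 change in those excluded, the placebo mean stays at −8.00 and the difference is again −7.60. In that case the shift comes wholly from the outcome assumed for the excluded liraglutide subjects.

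**The case against.** **Few can be excluded.** Any efficacy endpoint meets the second condition, so one blood pressure or weight at week 1 is enough. Most losses during dose escalation therefore stay in the FAS. Early stoppers have further routes in: Premature discontinuation asks for a visit that records body weight, and Visit Procedures asks for end-of-treatment procedures at withdrawal and for Visit 16x. This stands, and it keeps the practical effect small.

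**The set is disclosed and defended.** One may say that the FAS definition simply states what the protocol means by intention to treat. That does not reconcile it with Subject Replacement. The appeal to FDA recommendations cannot be checked from the documents, covers only the post-baseline condition, and would not make the set intention to treat.

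**The stronger reading.** A reader might infer that drug intolerance during escalation removes more liraglutide subjects and so biases the estimate towards benefit, by something like 0.2 to 1.0 points. The documents do not support this:

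- The 47.6% nausea figure under Tolerability and Adverse Events is for 3.0 mg, has no placebo comparator and is not loss to follow-up. The exclusion window is mainly the first week, at 0.6 mg.
- The same section gives nearly equal withdrawal rates, about 8.5% on liraglutide and 8.6% on placebo. These cover whole trials, so they do not rule out an early imbalance, but they give no evidence for one.
- Allocation is blinded, so failing to take a first dose should hardly depend on arm.
- An all-randomised analysis would not by itself produce the illustrated shift. Subjects with no post-baseline data add essentially nothing to a mixed model, and within-arm imputation under missing at random places them near their arm's mean. Only baseline carried forward or a not-at-random assumption would move the estimate that way.

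**Conclusion.** The contradiction is established from the text alone. The set labelled intention to treat carries two post-randomisation conditions that Statistical Methods and Subject Replacement do not, and no all-randomised set exists. Followed as written, the FAS would discard a never-dosed subject's week-40 VAT and would treat two subjects with the same VAT data differently.

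The number affected is probably small. This rests on efficacy endpoints being collected from week 1 and on the discontinuation visits taking place as planned. Bias towards liraglutide is possible if very early loss differs by arm, but it is not shown, and its size cannot be computed from the documents. The definition should be corrected because the label is wrong, measured outcomes can be lost, and the correction is cheap. No case is made that the result would be materially distorted.

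**What to change.** - Define the primary analysis set as all randomised subjects, analysed as assigned regardless of exposure.
- Use every week-40 VAT obtained at Visit 16 or Visit 16x.
- Handle missing week-40 VAT with the planned missing-data method. Add a sensitivity analysis under a not-missing-at-random assumption, for example no change or a placebo-like change for subjects without post-baseline data.
- Keep the present FAS as a sensitivity set labelled modified intention to treat, and keep the exposed set for safety.
- Align Subject Replacement, Statistical Methods and Evaluability of Subjects. Also reconcile Premature discontinuation, which offers end-of-trial imaging only after at least 40 weeks of treatment, with the sections that ask all early discontinuers to return at week 40. Without that, the all-randomised analysis will lack data it could have had.

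The cost is one definition and matching wording, a few more subjects with imputed values, and possibly a slightly less favourable estimate. The sample sizes of 128 and 178 stay as they are.
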